Administration of the study treatment will be discontinued in the event of a TEAE that persists despite appropriate dose modifications or any other AE that, in the opinion of the Investigator, warrants discontinuation.

Ramucirumab or tusamitamab ravtansine can be discontinued prematurely. The patient will remain on study treatment until the last IMP can be discontinued for disease progression, unacceptable AE, or the participant's or investigator's decision to stop the treatment. The reason for premature discontinuation will be captured in the appropriate eCRF page.

Dose modifications different from those stated in the protocol should be made only in consultation with the Sponsor unless required for immediate participant safety.

All changes to study treatment administration must be recorded in the eCRF.

In the event of neutropenia or febrile neutropenia, therapeutic G-CSF should be administered according to the current American Society of Clinical Oncology (ASCO) guidelines ([13](#)); for specific recommendations for this study, refer to Appendix 6 ([Section 10.6](#)).

The acceptable treatment window for tusamitamab ravtansine and ramucirumab administration is ± 2 days.

See Appendix 6 in [Section 10.6](#) for further guidance for dose modification or discontinuation. Approved product labels for ramucirumab should be followed for supportive care and dose modification requirement due AEs not listed in [Section 10.6](#). During the conduct of the study, a second dose reduction may be needed; such an action must be decided in a case-by-case discussion with the Sponsor. In case a dose reduction is necessary for Cycle 2 and subsequent cycles, the study intervention will be administered as follows in [Table 7](#).

Table 7 - Dose modification for toxicity

Drug name	Dose	1 st dose reduction ^a	2 nd dose reduction ^a
tusamitamab ravtansine	100 mg/m ² Q2W	80 mg/m ² Q2W	(not permitted)
ramucirumab	8 mg/kg Q2W	6 mg/kg Q2W	5 mg/kg Q2W

^a Dose modification is applicable from Cycle 2. At Cycle 1 the dose will remain the recommended dose (170 mg/m² or 150 mg/m²).

Any participant who requires a tusamitamab ravtansine or ramucirumab dose reduction will continue to receive a reduced dose until discontinuation from tusamitamab ravtansine/ramucirumab or discontinuation from the study.

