Ocular toxicity (continued)	Grade 3 Symptomatic with marked decrease in visual acuity (best corrected visual acuity worse than 20/40 or more than 3 lines of decreased vision from known baseline, up to 20/200); corneal ulcer; limiting selfcare activity of daily life	Administer ramucirumab at same dose, and same day as tusamitamab ravtansine or administer ramucirumab as planned if definitive discontinuation of tusamitamab ravtansine	1 st episode: Omit tusamitamab ravtansine until resolution (asymptomatic), and restart tusamitamab ravtansine with dose reduction. 2 nd episode: definitive discontinuation of tusamitamab ravtansine.	Standard ocular examination weekly until resolution ^{c, d} Start curative treatment per ophthalmologist recommendation. After resuming study treatment, participant should be followed with standard ocular examination by every 2 cycles, e en asymptomatic during next four cycles. If no recurrence, standard process with follow-up with ocular symptom is resumed Management of study drug upon recurrence to be discussed according to Grade of the event at recurrence, clinical benefit from study drug and recommendation from the ophthalmologist
	Grade 4 Perforation or best corrected visual acuity of 20/200 or worse in the affected eye.	Administer ramucirumab as planned.	Definitive discontinuation of tusamitamab ravtansine.	Complete the corneal examination as recommended by ophthalmologist. Repeat the standard ocular examination weekly ^c until resolution ^d . Start curative treatment per ophthalmologist recommendation.
Conduction disorder associated with tusamitamab ravtansine	Grade 1 Mild symptoms	Administer ramucirumab as planned.	tusamitamab ravtansine administration to be continued upon decision by the Investigator and Sponsor, depending on the nature of the conduction disorder.	ECG performed once weekly until event resolution. Additional evaluations such as LVEF and Holter monitoring should be performed when relevant.
	Grade ≥2	Administer ramucirumab as planned.	Definitive discontinuation of tusamitamab ravtansine.	ECG to be repeated twice weekly until event resolution. Prompt cardiology consultation Additional evaluations such LVEF and Holter monitoring should be performed when relevant.

Event	Symptoms severity (Nadir) (NCI CTCAE v5)	Management of IMP dosing (ramucirumab)	Management of IMP dosing (tusamitamab ravtansine)	Supportive care guidelines

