Peripheral neuropathy	Grade 1: Asymptomatic	Administer ramucirumab as planned.	Administer tusamitamab ravtansine as planned,	Patient who has ongoing Grade 1 neuropathy has high risk of worsening of his/her symptoms and should be closely followed.
	Grade 2: Moderate symptoms; limiting instrumental Activities of Daily Living	Delay cycle until recovery to \leq Grade 1; at next cycle, administer ramucirumab the same day as tusamitamab ravtansine	Delay cycle until recovery to \leq Grade 1 and dose reduction if no improvement with dose delay	
	Grade 3: Severe symptoms; limiting self care Activities of Daily Living	Administer ramucirumab as planned.	Definitive discontinuation of tusamitamab ravtansine	
	Grade 4: Life-threatening consequences; urgent intervention indicated	Administer ramucirumab as planned.	Definitive discontinuation of tusamitamab ravtansine	
Neutrophil count decreased	Grade 1 <LLN - 1500/mm ³ ; <LLN - 1.5 × 10 ⁹ /L	No change in IMPs administration.	No change in IMPs administration	No intervention.
	Grade 2 <1500 - 1000/mm ³ ; <1.5 - 1.0 × 10 ⁹ /L	Delay the cycle until recovery of absolute neutrophil count >1500/mm ³ . Restart at the same dose.	Delay the cycle until recovery of absolute neutrophil count >1500/mm ³ . Restart at the same dose.	No intervention.
	Grade 3 <1000 - 500/mm ³ ; <1.0 - 0.5 × 10 ⁹ /L Or	Delay the cycle until recovery of absolute neutrophil count >1500/mm ³ . Restart when absolute neutrophil count >1500/mm ³ at the same dose. Prophylactic G-CSF can be considered in all subsequent cycles	Delay the cycle. Restart the treatment when absolute neutrophil count >1500/mm ³ at the same dose; prophylactic G-CSF can be considered in all subsequent cycles	Follow ASCO guidelines on usage of G-CSF and antibiotherapy (13). Repeat test every 3 days.
	Grade 4 <500/mm ³ ; <0.5 × 10 ⁹ /L			

Event	Symptoms severity (Nadir) (NCI CTCAE v5)	Management of IMP dosing (ramucirumab)	Management of IMP dosing (tusamitamab ravtansine)	Supportive care guidelines

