Neutrophil count decreased (continued)	Grade 4 >7 days <500/mm ³ ; <0.5 × 10 ⁹ /L	Delay the cycle until absolute neutrophil count >1500/mm ³ . 1st episode administer next cycle with ramucirumab at the same dose and administer growth factors 2nd episode: administer ramucirumab at the same dose 3rd episode: definitive discontinuation of IMPs	Delay the cycle until absolute neutrophil count >1500/mm ³ . 1 st episode administer tusamitamab ravtansine next cycle at the same dose and administer growth factors 2 nd episode: administer tusamitamab ravtansine at reduced dose 3 rd episode: definitive discontinuation	Follow ASCO guidelines on G-CSF usage and antibiotherapy (13). Repeat test every 3 days.
Febrile neutropenia	Grade 3 Absolute neutrophil count <1000/mm ³ with a single temperature of >38.3°C (101°F) or a sustained temperature of ≥38°C (100.4°F) for more than 1 hour	Delay cycle until absolute neutrophil count >1500/mm ³ . 1st episode administer next cycle at the same dose and administer G-CSF 2nd episode: administer ramucirumab at reduce dose 3rd episode: definitive discontinuation	Delay cycle until absolute neutrophil count >1500/mm ³ . 1 st episode administer next cycle at the same dose and administer G-CSF 2 nd episode: administer tusamitamab ravtansine at reduce dose 3 rd episode: definitive discontinuation	To ensure relative dose intensity, G-CSF is recommended as secondary prophylaxis in all patients with Grade 3 febrile neutropenia ASCO guideline is recommended for supportive treatment if there are no defined clinical standards (13).
	Grade 4 Life-threatening consequences	Administration changes to be decided at the Investigator's discretion per product label	Administration changes to be decided at the Investigator's discretion. 1 st episode: administer next cycle at reduced dose and administer G-CSF 2 nd episode: definitive discontinuation	
Hypertension	Grade 3 Severe hypertension	Withhold ramucirumab until controlled with medical management, and restart at same dose	Administer tusamitamab ravtansine the same day as ramucirumab	
	Grade 4 Severe hypertension that cannot be controlled with antihypertensive therapy	Definitively discontinue ramucirumab	Administer tusamitamab ravtansine as planned	

Event	Symptoms severity (Nadir) (NCI CTCAE v5)	Management of IMP dosing (ramucirumab)	Management of IMP dosing (tusamitamab ravtansine)	Supportive care guidelines

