• Dose reduction: The first administration (loading dose) and second administration (first 100 mg/m^2 infusion) will not be counted as a dose reduction. For the third and subsequent tusamitamab ravtansine administrations, dose reduction will be determined using the dose level intervals provided in Table 5, by comparing the current dose level to the previous dose level. If the current dose level is below the dose level interval of the previous dose administration, then the current dose level is considered reduced.

Actual dose level	Dose level interval
Starting dose (100 mg/m  )	>90 mg/m²
Dose level -1 (80 mg/m  )	>72.5 mg/m² and ≤90 mg/m²
Low dose	>0 mg/m² and ≤72.5 mg/m²

Table 5 - Tusamitamab ravtansine dose reduction criteria

- Dose delay: A dose will be considered as delayed if the tusamitamab ravtansine administration date of the current cycle 14 days tusamitamab ravtansine administration date of the previous cycle is >2 days. Dose delay is not defined for the first cycle.
- Dose omission is defined as a dose not administered at the scheduled visit but administered afterwards.
- Dose interruption: A dose will be considered as interrupted if the tusamitamab ravtansine administration is stopped during an infusion regardless of whether it is restarted or not.

Dose modifications and dose interruptions will be analyzed by participant and cycle as follows:

- **Participant** (number of participants treated will be used as denominator)
  - Number (%) of participants with at least 1 dose modification
    - Number (%) of participants with at least 1 dose delayed
    - Number (%) of participants with at least 1 dose reduction
    - Number (%) of participants with at least 1 dose omission
  - Number (%) of participants with a least 1 dose interruption

- Cycle (number of cycles started will be used as denominator)
  - Number (%) of cycles with at least 1 dose modification
    - Number (%) of cycles with at least 1 cycle delayed
    - Number (%) of cycles with at least 1 dose reduction
    - Number (%) of cycles with at least 1 dose omission
  - Number (%) of cycles with at least 1 dose interruption

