### 3.6.1.3 Ramucirumab exposure

The dose information will be assessed by the following:

- Total number of cycles started.
- Number of cycles started per participant.
- Duration of ramucirumab exposure (in weeks) is defined by date of last administration of ramucirumab + number of theoretical days until the next administration date of first administration of ramucirumab/7.
- Actual dose (in mg/kg). In case of dose interruption, actual dose will be the sum of the actual doses administered before and after the dose interruption.
- Cumulative dose (mg/kg): the cumulative dose is the sum of all actual doses of ramucirumab, given from first to last administration.
- Actual dose intensity (ADI in mg/kg/week): defined as the cumulative dose divided by the duration of ramucirumab exposure (in weeks).
- Planned dose intensity (PDI in mg/kg/week): corresponds to the planned dose multiplied by the theoretical total number of doses started and divided by the theoretical cycle duration expressed in weeks (ie, 2 weeks per cycle started). Note: Theoretical total number of doses started is derived based on cycles where at least one IMP is administered (even in case of dose omission), up to the end of treatment of ramucirumab.
- Relative dose intensity (RDI, in %):100  $\times \frac{\text{ADI (mg/kg/week)}}{\text{PDI (mg/kg/week)}}$ .

The total number of cycles started, number of cycles started by participant will be summarized as a quantitative variable and by category (number [%] of participants receiving at least 1 cycle, at least 2 cycles, etc). Duration of ramucirumab exposure, cumulative dose, ADI and RDI will be summarized quantitatively.

The following variables will be derived to describe dose modifications and dose interruptions:

• Dose reduction: The first administration will not be counted as a dose reduction. For the second and subsequent ramucirumab administrations, dose reduction will be determined using the dose level intervals provided in Table 6, by comparing the current dose level to the previous dose level. If the current dose level is below the dose level interval of the previous dose administration, then the current dose level is considered reduced.

Actual dose level	Dose level interval
Starting dose (8 mg/kg)	>7 mg/kg
Dose level -1 (6 mg/kg)	>5.5 mg/kg and ≤7 mg/kg
Dose level -2 (5 mg/kg)	> 4 mg/kg and ≤5.5 mg/kg
Low dose	>0 mg/kg and ≤4 mg/kg

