#### Table 9 - Selections for AESIs and other AEs of interest

An overview of corneal TEAEs will be provided with the following AE categories: any corneal TEAEs, Grade  $\geq$ 3 corneal TEAEs, treatment-emergent corneal SAEs, corneal TEAEs related to IMP, Grade  $\geq$ 3 corneal TEAEs related to IMP, corneal TEAEs leading to permanent full intervention discontinuation, corneal TEAEs leading to permanent partial discontinuation of tusamitamab ravtansine, and corneal TEAEs leading to dose modification (cycle delay, dose reduction, or dose omission) of tusamitamab ravtansine.

A summary of treatment-emergent corneal events will be provided.

- Cycle of first occurrence regardless of the grade
- Cycle of first occurrence of the worst grade
- Number (%) of participants by worst grade
- Relationship to study intervention: in case of multiple occurrences in a single participant with different relationships, if any event is related, then the relationship will be considered as related for that participant
- Action taken with the study intervention: in case of multiple occurrences with different actions in a single participant, the most severe action taken will be tabulated and selected according to the following order of severity: drug withdrawn, dose reduced, drug interrupted, dose not changed
- Outcome: in case of multiple occurrences with different outcomes in a single participant, the most severe outcome will be tabulated and selected according to the following order of severity: fatal, not recovered or resolved, recovering and resolving, recovered and resolved with sequelae, recovered and resolved, unknown.

In addition, analyses on occurrence and recurrence of corneal events will be provided. An occurrence of a corneal event will be defined as 1 or a group of concomitant corneal events. A recurrence will be defined as any occurrence of corneal event starting after a previously resolved occurrence.

- The number of occurrences by participant
- The time to first onset of corneal event will be described using Kaplan-Meier curves. Time to first onset is defined as the time from the date of first IMP administration to the date of the first occurrence of the event. In the absence of an event before the analysis cut-off date, it will be censored at the end date of the treatment-emergent period, analysis cut-off date, or date of death, whichever occurs first.

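### SAP 3.6.1.2 never assesses the second tusamitamab ravtansine dose for a reduction, so a cut to 80 mg/m² at that dose is missing from the derived dose-reduction count

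*SAP*

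**What the plan says.** SAP 3.6.1.2 states that the first administration (the loading dose) and the second, which it describes in parentheses as the first infusion at 100 mg/m², are not counted as reductions. It continues: "For the third and subsequent tusamitamab ravtansine administrations, dose reduction will be determined using the dose level intervals provided in Table 5". The comparison is with the previous dose level. Table 5 has three intervals: above 90 mg/m², above 72.5 and up to 90 mg/m², and above 0 and up to 72.5 mg/m².

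The ramucirumab rule in SAP 3.6.1.3 begins one dose earlier: "For the second and subsequent ramucirumab administrations, dose reduction will be determined using the dose level intervals provided in Table 6".

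Protocol 6.5, Table 7, gives 80 mg/m² as the one reduced level below 100 mg/m². Its footnote says "Dose modification is applicable from Cycle 2". The text after the table says that a participant who needs a reduction "will continue to receive a reduced dose until discontinuation".

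Protocol Appendix 6 has three events that can lead to a reduced tusamitamab ravtansine dose at the first episode:
- Grade 3 keratopathy: "Omit tusamitamab ravtansine until resolution (asymptomatic), and restart tusamitamab ravtansine with dose reduction"
- Grade 2 peripheral neuropathy: delay, then "dose reduction if no improvement with dose delay"
- Grade 4 febrile neutropenia: "administer next cycle at reduced dose and administer G-CSF"

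**The concern.** The protocol allows the first reduction at exactly the dose that the SAP does not assess. Because the reduced dose is then kept, every later comparison is 80 against 80, and the missed step is never recovered.

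The outputs at stake are descriptive:
- **Dose-reduction lines.** The cycle-level count is one too low for each case. The participant-level line is too low unless a later dose falls to 72.5 mg/m² or less and is counted then.
- **Dose-modification lines.** These can be wrong only if the reduced second dose was neither delayed by more than 2 days nor omitted. That group is narrow: of the three Appendix 6 routes, keratopathy states an omission and neuropathy a delay; only Grade 4 febrile neutropenia states neither.
- **PK summaries.** SAP 3.7.1.1 takes its definition of a reduction from 3.6.1.2 when it excludes concentrations from the descriptive statistics, so some that should be excluded would be kept.

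The gap lies at the dose straight after the loading dose, whose tolerability Part 1 is meant to confirm, and the error always runs towards under-reporting.

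**Working it through.** The plan states no expected number of reductions, so there is no figure to reproduce. The check applies the written rule to dose sequences.

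**Inputs.** Table 5 intervals (SAP 3.6.1.2): A is above 90, B is above 72.5 to 90, C is above 0 to 72.5 mg/m². Loading dose 170 or 150 mg/m², then 100 mg/m² (SAP 1.1). Reduced level 80 mg/m² from Cycle 2, kept thereafter (Protocol 6.5). Treated participants: 32 to 38 (SAP 1.1). Median treatment 18 weeks in 14-day cycles (SAP 1.1).

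**Rule.** Administration k counts as a reduction if its interval is lower than that of administration k−1. The SAP applies this for k ≥ 3; the alternative applies it for k ≥ 2.

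| Doses (mg/m²) | Intervals | SAP rule (k ≥ 3) | From second dose (k ≥ 2) |
|---|---|---|---|
| 170-100-100-100 | A A A A | 0 | 0 |
| 150-100-100-100 | A A A A | 0 | 0 |
| 170-100-80-80 | A A B B | 1 | 1 |
| 170-80-80-80 | A B B B | 0 | 1 |
| 150-80-80-80 | A B B B | 0 | 1 |
| 170-80-80-70 | A B B C | 1 | 2 |

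Rows 1 and 2 show that assessing the second dose does not flag the planned step-down. Rows 3 and 4 show the same cut counted or missed according to whether it falls at dose 3 or dose 2. In row 6 the later fall is caught, so the participant-level line is right, but the first cut is still lost. Ramucirumab 8-6-6-6 mg/kg under SAP Table 6 gives 1.

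**Size per missed participant.**
- Participant level: 1/38 = 2.6% to 1/32 = 3.1%.
- Cycle level, assuming 18/2 = 9 cycles for everyone: 1/(38 × 9) = 1/342 = 0.29% to 1/(32 × 9) = 1/288 = 0.35%.

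**What still shows the cut.** With five on-time doses of 170-80-80-80-80, relative dose intensity is (170 + 4 × 80)/(170 + 4 × 100) = 490/570 = 86.0%.

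**PK samples wrongly kept after a reduced Cycle 2 dose.** SAP 3.7.1.1 excludes troughs after a delay or a reduction, and end-of-infusion samples after a reduction only. It does not say whether the exclusion covers the next sample or all later ones. Sampling times are from Protocol 1.3.2.

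| Reduced Cycle 2 dose | Next sample only | All later samples |
|---|---|---|
| On schedule | Cycle 3 trough | Troughs at Cycles 3, 4, 5, 6, 7 and 13, and the Cycle 4 sample 1 hour after end of infusion |
| Delayed by more than 2 days | None | Cycle 4 sample 1 hour after end of infusion (the delay already excludes the troughs) |

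The later samples matter only for participants still on treatment and being sampled; Cycle 13 starts at week 24 on schedule, after the planned median.

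**The case against.** The strongest reply is that the SAP describes the second administration as the first 100 mg/m² infusion, so the exemption was written for a second dose given at 100 and a second dose of 80 was simply not considered. That is probably how the wording arose. It does not close the gap, because assessment still starts at the third administration and no other rule covers a second dose of 80.

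The second reply is that few participants will be affected. Protocol 4.3 reports that the DLTs in the main escalation phase of the first-in-human study were keratopathies at the end of Cycle 2; a reduction after those falls at the third dose, where the rule works. The retreatment criteria in Protocol 6.5.1 also make an on-schedule reduced second dose after Grade 4 febrile neutropenia less likely. Both points stand and limit the expected size.

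The third reply is that the information is not lost. Relative dose intensity, the SAP Table 8 summary of TEAEs leading to dose modification, and the corneal overview, which includes "corneal TEAEs leading to dose modification (cycle delay, dose reduction, or dose omission) of tusamitamab ravtansine", would all still show the case. Grade 3 or higher keratopathy and DLTs are also reported as AESIs. This stands too: what is wrong is a derived count, not the safety record.

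Finally, actual dose in SAP 3.6.1.2 is the amount infused, so a second 100 mg/m² infusion stopped early could be flagged as a reduction. That is true, but the existing rule from the third dose and the ramucirumab rule already behave this way.

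**Conclusion.** The concern holds, at minor severity. As written, the rule gives zero reductions for a participant cut to 80 mg/m² at the second administration and kept there, and one for the same cut a dose later. Each such participant lowers the participant-level rate by 2.6 to 3.1 percentage points, with 32 to 38 treated, and the cycle-level rate by about 0.3 points if everyone receives 9 cycles. These are sizes per case, not an expected effect: the documents do not allow the number of cases to be estimated.

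The PK effect is confined to descriptive concentration summaries and depends on how the exclusion in SAP 3.7.1.1 is read. The DLT endpoint and all efficacy analyses are unaffected.

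**What to change.** In SAP 3.6.1.2, exempt only the first administration. Count the second as a reduction if the actual dose is 90 mg/m² or less, that is, below the top interval of Table 5. Keep the comparison with the previous dose from the third administration onward. Use the same flag for the PK exclusions in SAP 3.7.1.1.

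The cost is one SAP sentence and one line of programming. The planned step from 170 or 150 to 100 mg/m² remains unflagged, the rule then starts at the same administration as the ramucirumab rule, and the reported reduction count can only stay the same or rise. No dosing rule changes.
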